	Likely Unrelated	xx ( xx.x%)	xx ( xx.x%)

<sup>a Counts reflect numbers of subjects reporting one or more TEAEs that map to the MedDRA. At each level of summarization (System Organ Class or Preferred Term) subjects are counted once under the greatest reported relationship.

Note: TEAEs are AEs with an onset after first dose of study drug.

MedDRA Version 21.1.

Table 14.3.1.4.1.1: Summary of Hematology Laboratory Results (Safety Population)
(Page 1 of xx)

	Placebo	Serlopitant 5 mg
	(N=xxx)	(N=xxx)
<test name=""> (<units>)</units></test>		
Baseline		
n	XX	XX
Mean	XX.X	XX.X
SD	XX.XX	XX.XX
Median	XX.X	XX.X
Min. to Max.	xx to xx	xx to xx
Week 2		
n	XX	XX
Mean	XX.X	XX.X
SD	XX.XX	XX.XX
Median	XX.X	XX.X
Min. to Max.	xx to xx	xx to xx
Absolute Change from Baseline		
n	XX	XX
Mean	XX.X	XX.X
SD	XX.XX	XX.XX
Median	XX.X	XX.X
Min. to Max.	xx to xx	xx to xx

Note: No imputation of missing values. Baseline is the latest recorded value prior to first dose of study drug. Change calculated as post-baseline – baseline. "Latest Follow-up" visit includes the latest available follow-up information for each subject from the 3-Week or 5-Week Follow-up visits.

SOURCE: USERNAME\SPONSOR\PROJECT\JOBNAME (DATE,TIME)

Table to include post-baseline visits of "Week 2", "Week 10", "3-Week Follow-up", "5-Week Follow-up", "Latest Follow-up".

Table to include following lab tests: "BASOPHILS", "EOSINOPHILS", "HCT", "HGB", "LYMPHOCYTES", "MCH", "MCHC", "MCV", "MONOCYTES", "NEUTROPHILS", "PLATELET COUNT", "RBC", "WBC".

Table 14.3.1.4.1.2: Shift Summary of Hematology Laboratory Results (Safety Population)
(Page 1 of xx)

<test name=""> (<units>)</units></test>		Placebo (N=xxx)			Serlopitant 5 mg (N=xxx)	
		Week 2			Week 2	
Baseline	BNL	WNL	ANL	BNL	WNL	ANL
BNL	xx (xx.x%)	xx ( xx.x%)	xx ( xx.x%)	xx ( xx.x%)	xx ( xx.x%)	xx ( xx.x%)
WNL	xx ( xx.x%)	xx ( xx.x%)	xx ( xx.x%)	xx ( xx.x%)	xx ( xx.x%)	xx ( xx.x%)
ANL	xx ( xx.x%)	xx ( xx.x%)	xx ( xx.x%)	xx ( xx.x%)	xx ( xx.x%)	xx ( xx.x%)
		Week 10			Week 10	
Baseline	BNL	WNL	ANL	BNL	WNL	ANL
BNL	xx ( xx.x%)	xx ( xx.x%)	xx ( xx.x%)	xx ( xx.x%)	xx ( xx.x%)	xx ( xx.x%)
WNL	xx ( xx.x%)	xx ( xx.x%)	xx ( xx.x%)	xx ( xx.x%)	xx ( xx.x%)	xx ( xx.x%)
ANL	xx ( xx.x%)	xx ( xx.x%)	xx ( xx.x%)	xx ( xx.x%)	xx ( xx.x%)	xx ( xx.x%)
	3-	-Week Follow-up		3-	Week Follow-up	
Baseline	BNL	WNL	ANL	BNL	WNL	ANL
BNL	xx ( xx.x%)	xx ( xx.x%)	xx ( xx.x%)	xx ( xx.x%)	xx ( xx.x%)	xx ( xx.x%)
WNL	xx ( xx.x%)	xx ( xx.x%)	xx ( xx.x%)	xx ( xx.x%)	xx ( xx.x%)	xx ( xx.x%)
ANL	xx ( xx.x%)	xx ( xx.x%)	xx ( xx.x%)	xx ( xx.x%)	xx ( xx.x%)	xx ( xx.x%)
		-Week Follow-up			Week Follow-up	
Baseline	BNL	WNL	ANL	BNL	WNL	ANL
BNL	xx ( xx.x%)	xx ( xx.x%)	xx ( xx.x%)	xx ( xx.x%)	xx ( xx.x%)	xx ( xx.x%)
WNL	xx ( xx.x%)	xx ( xx.x%)	xx ( xx.x%)	xx ( xx.x%)	xx ( xx.x%)	xx ( xx.x%)
ANL	xx ( xx.x%)	xx ( xx.x%)	xx ( xx.x%)	xx ( xx.x%)	xx ( xx.x%)	xx ( xx.x%)
		_atest Follow-up			atest Follow-up	
Baseline	BNL	WNL	ANL	BNL	WNL	ANL
BNL	xx ( xx.x%)	xx ( xx.x%)	xx ( xx.x%)	xx ( xx.x%)	xx ( xx.x%)	xx ( xx.x%)
WNL	xx ( xx.x%)	xx ( xx.x%)	xx ( xx.x%)	xx ( xx.x%)	xx ( xx.x%)	xx ( xx.x%)
ANL	xx ( xx.x%)	xx ( xx.x%)	xx ( xx.x%)	xx ( xx.x%)	xx ( xx.x%)	xx ( xx.x%)

Note: BNL=Below Normal Limit, WNL=Within Normal Limits, ANL=Above Normal Limit.

No imputation of missing values. Baseline is the latest recorded value prior to first dose of study drug. "Latest Follow-up" visit includes the latest available follow-up information for each subject from the 3-Week or 5-Week Follow-up visits.

SOURCE: USERNAME\SPONSOR\PROJECT\JOBNAME (DATE,TIME)

Table to include the same lab tests used in Table 14.3.1.4.1.1.

Statistical Analysis Plan for Menlo Therapeutics Inc. Protocol Number: MTI-105

Table 14.3.1.4.2.1: Summary of Chemistry Laboratory Results (Safety Population)
(Page 1 of xx)

	Placebo	Serlopitant 5 mg
	(N=xxx)	(N=xxx)
<test name=""> (<units>)</units></test>		
Baseline		
n	XX	XX
Mean	XX.X	XX.X
SD	XX.XX	XX.XX
Median	XX.X	XX.X
Min. to Max.	xx to xx	xx to xx
Week 2		
n	XX	XX
Mean	XX.X	XX.X
SD	XX.XX	XX.XX
Median	XX.X	XX.X
Min. to Max.	xx to xx	xx to xx
Absolute Change from Baseline		
n	XX	XX
Mean	XX.X	XX.X
SD	XX.XX	XX.XX
Median	XX.X	XX.X
Min. to Max.	xx to xx	xx to xx

Note: No imputation of missing values. Baseline is the latest recorded value prior to first dose of study drug. Change calculated as post-baseline – baseline. "Latest Follow-up" visit includes the latest available follow-up information for each subject from the 3-Week or 5-Week Follow-up visits.

SOURCE: USERNAME\SPONSOR\PROJECT\JOBNAME (DATE,TIME)

Table to include post-baseline visits of "Week 2", "Week 10", "3-Week Follow-up", "5-Week Follow-up", "Latest Follow-up".

Table to include following lab tests: "ALBUMIN", "ALKALINE PHOSPHATASE", "ALT", "AST", "BICARBONATE", "BILIRUBIN, TOTAL", "BUN", "CALCIUM", "CHLORIDE", "CHOLESTEROL, TOTAL", "CREATININE", "GLUCOSE, RANDOM", "HDL-CHOLESTEROL", "LDH", "LDL-CHOLESTEROL", "MAGNESIUM", "PHOSPHORUS", "POTASSIUM", "PROTEIN, TOTAL", "SODIUM", "TRIGLYCERIDES", "URIC ACID".

Statistical Analysis Plan for Menlo Therapeutics Inc. Protocol Number: MTI-105

Table 14.3.1.4.2.2: Shift Summary of Chemistry Laboratory Results (Safety Population)
(Page 1 of xx)

<test name=""> (<units>)</units></test>		Placebo (N=xxx)			Serlopitant 5 mg (N=xxx)	
		Week 2			Week 2	
Baseline	BNL	WNL	ANL	BNL	WNL	ANL
BNL	xx (xx.x%)	xx ( xx.x%)	xx ( xx.x%)	xx ( xx.x%)	xx ( xx.x%)	xx ( xx.x%)
WNL	xx (xx.x%)	xx ( xx.x%)	xx ( xx.x%)	xx ( xx.x%)	xx ( xx.x%)	xx ( xx.x%)
ANL	xx ( xx.x%)	xx ( xx.x%)	xx ( xx.x%)	xx ( xx.x%)	xx ( xx.x%)	xx ( xx.x%)
		Week 10			Week 10	
Baseline	BNL	WNL	ANL	BNL	WNL	ANL
BNL	xx ( xx.x%)	xx ( xx.x%)	xx ( xx.x%)	xx ( xx.x%)	xx ( xx.x%)	xx ( xx.x%)
WNL	xx ( xx.x%)	xx ( xx.x%)	xx ( xx.x%)	xx ( xx.x%)	xx ( xx.x%)	xx ( xx.x%)
ANL	xx ( xx.x%)	xx ( xx.x%)	xx ( xx.x%)	xx ( xx.x%)	xx ( xx.x%)	xx ( xx.x%)
	3-	-Week Follow-up		3-	-Week Follow-up	
Baseline	BNL	WNL	ANL	BNL	WNL	ANL
BNL	xx ( xx.x%)	xx ( xx.x%)	xx ( xx.x%)	xx ( xx.x%)	xx ( xx.x%)	xx ( xx.x%)
WNL	xx ( xx.x%)	xx ( xx.x%)	xx ( xx.x%)	xx ( xx.x%)	xx ( xx.x%)	xx ( xx.x%)
ANL	xx ( xx.x%)	xx ( xx.x%)	xx ( xx.x%)	xx ( xx.x%)	xx ( xx.x%)	xx ( xx.x%)
		-Week Follow-up			-Week Follow-up	
Baseline	BNL	WNL	ANL	BNL	WNL	ANL
BNL	xx ( xx.x%)	xx ( xx.x%)	xx ( xx.x%)	xx ( xx.x%)	xx ( xx.x%)	xx ( xx.x%)
WNL	xx ( xx.x%)	xx ( xx.x%)	xx ( xx.x%)	xx ( xx.x%)	xx ( xx.x%)	xx ( xx.x%)
ANL	xx ( xx.x%)	xx ( xx.x%)	xx ( xx.x%)	xx ( xx.x%)	xx ( xx.x%)	xx ( xx.x%)
		_atest Follow-up			_atest Follow-up	
Baseline	BNL	WNL	ANL	BNL	WNL	ANL
BNL	xx ( xx.x%)	xx ( xx.x%)	xx ( xx.x%)	xx ( xx.x%)	xx ( xx.x%)	xx ( xx.x%)
WNL	xx ( xx.x%)	xx ( xx.x%)	xx ( xx.x%)	xx ( xx.x%)	xx ( xx.x%)	xx ( xx.x%)
ANL	xx ( xx.x%)	xx ( xx.x%)	xx ( xx.x%)	xx ( xx.x%)	xx ( xx.x%)	xx ( xx.x%)

Note: BNL=Below Normal Limit, WNL=Within Normal Limits, ANL=Above Normal Limit.

No imputation of missing values. Baseline is the latest recorded value prior to first dose of study drug. "Latest Follow-up" visit includes the latest available follow-up information for each subject from the 3-Week or 5-Week Follow-up visits.

SOURCE: USERNAME\SPONSOR\PROJECT\JOBNAME (DATE,TIME)

Table to include the same lab tests used in Table 14.3.1.4.2.1.

Table 14.3.1.4.3.1.1: Summary of Endocrine/Reproductive Endocrine Laboratory Results (Safety Population)
(Page 1 of xx)

	Placebo	Serlopitant 5 mg
	(N=xxx)	(N=xxx)
<test name=""> (<units>)</units></test>		•
Baseline		
n	XX	XX
Mean	XX.X	XX.X
SD	XX.XX	XX.XX
Median	XX.X	XX.X
Min. to Max.	xx to xx	xx to xx
Week 10		
n	XX	XX
Mean	XX.X	XX.X
SD	XX.XX	XX.XX
Median	XX.X	XX.X
Min. to Max.	xx to xx	xx to xx
Absolute Change from Baseline		
n	XX	XX
Mean	XX.X	XX.X
SD	XX.XX	XX.XX
Median	XX.X	XX.X
Min. to Max.	xx to xx	xx to xx

Note: No imputation of missing values. Baseline is the latest recorded value prior to first dose of study drug. Change calculated as post-baseline – baseline. "Latest Follow-up" visit includes the latest available follow-up information for each subject from the 3-Week or 5-Week Follow-up visits. SOURCE: USERNAME\SPONSOR\PROJECT\JOBNAME (DATE,TIME)

Table to include post-baseline visits of "Week 10", "3-Week Follow-up", "5-Week Follow-up", "Latest Follow-up".

Table to include following lab tests: "TSH ULTRASENSITIVE", "THYROXINE, FREE", "CORTISOL, SERUM RANDOM", "ACTH, PLASMA", "ANTI-MULLERIAN HORMONE", "FSH", "ESTRADIOL", "LUTEINIZING HORMONE", "PROGESTERONE".

Table 14.3.1.4.3.1.2: Summary of Reproductive Endocrine Laboratory Results (Safety Population – Females Using Hormonal Contraception/Therapy) (Page 1 of xx)

	Placebo	Serlopitant 5 mg
	N=xxx	(N=xxx)
<test name=""> (<units>)</units></test>		
Baseline		
n	XX	XX
Mean	XX.X	XX.X
SD	XX.XX	XX.XX
Median	XX.X	XX.X
Min. to Max.	xx to xx	xx to xx
Week 10		
n	XX	XX
Mean	XX.X	XX.X
SD	XX.XX	XX.XX
Median	XX.X	XX.X
Min. to Max.	xx to xx	xx to xx
Absolute Change from Baseline		
n	XX	XX
Mean	XX.X	XX.X
SD	XX.XX	XX.XX
Median	XX.X	XX.X
Min. to Max.	xx to xx	xx to xx

Note: No imputation of missing values. Baseline is the latest recorded value prior to first dose of study drug. Change calculated as post-baseline – baseline. "Latest Follow-up" visit includes the latest available follow-up information for each subject from the 3-Week or 5-Week Follow-up visits.

SOURCE: USERNAME\SPONSOR\PROJECT\JOBNAME (DATE,TIME)

Table to include post-baseline visits of "Week 10", "3-Week Follow-up", "5-Week Follow-up", "Latest Follow-up".

Table to include following lab tests: "ANTI-MULLERIAN HORMONE", "FSH", "ESTRADIOL", "LUTEINIZING HORMONE", "PROGESTERONE".

Table 14.3.1.4.3.1.3: Summary of Reproductive Endocrine Laboratory Results (Safety Population – Females Not Using Hormonal Contraception/Therapy) (Page 1 of xx)

	Placebo	Serlopitant 5 mg
	(N=xxx)	(N=xxx)
<test name=""> (<units>)</units></test>		
Baseline		
n	XX	XX
Mean	XX.X	XX.X
SD	XX.XX	XX.XX
Median	XX.X	XX.X
Min. to Max.	xx to xx	xx to xx
Week 10		
n	XX	XX
Mean	XX.X	XX.X
SD	XX.XX	XX.XX
Median	XX.X	XX.X
Min. to Max.	xx to xx	xx to xx
Absolute Change from Baseline		
n	XX	XX
Mean	XX.X	XX.X
SD	XX.XX	XX.XX
Median	XX.X	XX.X
Min. to Max.	xx to xx	xx to xx

Note: No imputation of missing values. Baseline is the latest recorded value prior to first dose of study drug. Change calculated as post-baseline – baseline. "Latest Follow-up" visit includes the latest available follow-up information for each subject from the 3-Week or 5-Week Follow-up visits. SOURCE: USERNAME\SPONSOR\PROJECT\JOBNAME (DATE,TIME)

Table to include post-baseline visits of "Week 10", "3-Week Follow-up", "5-Week Follow-up", "Latest Follow-up".

Table to include following lab tests: "ANTI-MULLERIAN HORMONE", "FSH", "ESTRADIOL", "LUTEINIZING HORMONE", "PROGESTERONE".

Table 14.3.1.4.3.2: Shift Summary of Endocrine/Reproductive Endocrine Laboratory Results
(Safety Population)
(Page 1 of xx)

<test name=""> (<units>)</units></test>		Placebo (N=xxx)			Serlopitant 5 mg (N=xxx)	
		Week 10			Week 10	
Baseline	BNL	WNL	ANL	BNL	WNL	ANL
BNL	xx ( xx.x%)	xx ( xx.x%)	xx ( xx.x%)	xx ( xx.x%)	xx ( xx.x%)	xx ( xx.x%)
WNL	xx ( xx.x%)	xx ( xx.x%)	xx ( xx.x%)	xx ( xx.x%)	xx ( xx.x%)	xx ( xx.x%)
ANL	xx ( xx.x%)	xx ( xx.x%)	xx ( xx.x%)	xx ( xx.x%)	xx ( xx.x%)	xx ( xx.x%)
	3-	-Week Follow-up	,	3-	-Week Follow-up	` '
Baseline	BNL	WNL	ANL	BNL	WNL	ANL
BNL	xx ( xx.x%)	xx ( xx.x%)	xx ( xx.x%)	xx ( xx.x%)	xx ( xx.x%)	xx ( xx.x%)
WNL	xx ( xx.x%)	xx ( xx.x%)	xx ( xx.x%)	xx (xx.x%)	xx ( xx.x%)	xx ( xx.x%)
ANL	xx ( xx.x%)	xx ( xx.x%)	xx ( xx.x%)	xx (xx.x%)	xx ( xx.x%)	xx ( xx.x%)
	5.	-Week Follow-up		5-	-Week Follow-up	
Baseline	BNL	WNL	ANL	BNL	WNL	ANL
BNL	xx ( xx.x%)	xx ( xx.x%)	xx ( xx.x%)	xx ( xx.x%)	xx ( xx.x%)	xx ( xx.x%)
WNL	xx ( xx.x%)	xx ( xx.x%)	xx ( xx.x%)	xx ( xx.x%)	xx ( xx.x%)	xx ( xx.x%)
ANL	xx ( xx.x%)	xx ( xx.x%)	xx ( xx.x%)	xx ( xx.x%)	xx ( xx.x%)	xx ( xx.x%)
	I	Latest Follow-up		I	Latest Follow-up	 
Baseline	BNL	WNL	ANL	BNL	WNL	ANL
BNL	xx ( xx.x%)	xx ( xx.x%)	xx ( xx.x%)	xx ( xx.x%)	xx ( xx.x%)	xx ( xx.x%)
WNL	xx ( xx.x%)	xx ( xx.x%)	xx ( xx.x%)	xx ( xx.x%)	xx ( xx.x%)	xx ( xx.x%)
ANL	xx ( xx.x%)	xx ( xx.x%)	xx ( xx.x%)	xx ( xx.x%)	xx ( xx.x%)	xx ( xx.x%)

Note: BNL=Below Normal Limit, WNL=Within Normal Limits, ANL=Above Normal Limit.

No imputation of missing values. Baseline is the latest recorded value prior to first dose of study drug. "Latest Follow-up" visit includes the latest available follow-up information for each subject from the 3-Week or 5-Week Follow-up visits.

SOURCE: USERNAME\SPONSOR\PROJECT\JOBNAME (DATE,TIME)

Table to include following lab tests: "TSH ULTRASENSITIVE", "THYROXINE, FREE", "CORTISOL, SERUM RANDOM", "ACTH, PLASMA", "ANTI-MULLERIAN HORMONE".

Statistical Analysis Plan for Menlo Therapeutics Inc. Protocol Number: MTI-105

Table 14.3.1.5.1.1: Summary of Treatment-Emergent Electrocardiogram (ECG) Parameter Abnormalities (Safety Population)
(Page 1 of 2)

	Placebo	Serlopitant 5 mg
	(N=xxx)	(N=xxx)
number of Subjects with Treatment-Emergent ECG esults	XXX	XXX
R Interval		
> 200 msec	xx ( xx.x%)	xx ( xx.x%)
> 220 msec	xx ( xx.x%)	xx ( xx.x%)
hange from Baseline in PR Interval		
>= 25% and > 200 msec	xx ( xx.x%)	xx ( xx.x%)
RS Interval		
> 110 msec	xx ( xx.x%)	XX (XX.X%)
> 120 msec	xx ( xx.x%)	xx ( xx.x%)
hange from Baseline in QRS Interval		
>= 25% and > 110 msec	xx ( xx.x%)	xx (xx.x%)
>= 25% and > 120 msec	xx ( xx.x%)	xx ( xx.x%)
TcF Interval		
> 450 - 470 msec	xx ( xx.x%)	xx (xx.x%)
> 470 - 500 msec	xx ( xx.x%)	XX (XX.X%)
> 500 msec	xx ( xx.x%)	xx ( xx.x%)
hange from Baseline in QTcF Interval		
> 30 - 60 msec	xx ( xx.x%)	xx (xx.x%)
> 60 msec	xx ( xx.x%)	XX (XX.X%)
	,	,
TcF Interval > 500 msec and Change from Baseline > 60	xx ( xx.x%)	xx ( xx.x%)
sec		

Note: No imputation of missing values. Baseline is the latest recorded value prior to first dose of study drug. Change calculated as post-baseline – baseline. SOURCE: USERNAME\SPONSOR\PROJECT\JOBNAME (DATE,TIME)

Statistical Analysis Plan for Menlo Therapeutics Inc. Protocol Number: MTI-105

Table 14.3.1.5.1.1: Summary of Treatment-Emergent Electrocardiogram (ECG) Abnormalities (Safety Population)
(Page 2 of 2)

	Placebo (N=xxx)	Serlopitant 5 mg (N=xxx)
Number of Subjects with Treatment-Emergent ECG Results	xxx	xxx
QTcB Interval		
> 450 - 470 msec	xx ( xx.x%)	xx (xx.x%)
> 470 - 500 msec	xx ( xx.x%)	xx ( xx.x%)
> 500 msec	xx ( xx.x%)	xx ( xx.x%)
Change from Baseline in QTcB Interval		
> 30 - 60 msec	xx ( xx.x%)	xx (xx.x%)
> 60 msec	xx ( xx.x%)	xx ( xx.x%)
QTcB Interval > 500 msec and Change from Baseline > 60 msec	xx ( xx.x%)	xx ( xx.x%)

Note: No imputation of missing values. Baseline is the latest recorded value prior to first dose of study drug. Change calculated as post-baseline – baseline. SOURCE: USERNAME\SPONSOR\PROJECT\JOBNAME (DATE,TIME)

Table 14.3.1.5.1.2: Summary of Electrocardiogram Parameters (Safety Population)
(Page 1 of xx)

	Placebo	Serlopitant 5 mg
	(N=xxx)	(N=xxx)
<parameter> (<units>)</units></parameter>		
Baseline		
n	XX	XX
Mean	XX.X	XX.X
SD	XX.XX	XX.XX
Median	XX.X	XX.X
Min. to Max.	xx to xx	xx to xx
Week 2		
n	XX	XX
Mean	XX.X	XX.X
SD	XX.XX	XX.XX
Median	XX.X	XX.X
Min. to Max.	xx to xx	xx to xx
Absolute Change from Baseline		
n	XX	XX
Mean	XX.X	XX.X
SD	XX.XX	XX.XX
Median	XX.X	XX.X
Min. to Max.	xx to xx	xx to xx

Note: No imputation of missing values. Baseline is the latest recorded value prior to first dose of study drug. Change calculated as post-baseline – baseline. "Latest Follow-up" visit includes the latest available follow-up information for each subject from the 3-Week or 5-Week Follow-up visits. SOURCE: USERNAME\SPONSOR\PROJECT\JOBNAME (DATE,TIME)

Table to include parameters "ECG Mean Heart Rate (beats/min)", "PR Interval, Aggregate (msec)", "QRS Duration, Aggregate (msec)", "QT Interval, Aggregate (msec)", "QTcB Interval, Aggregate (msec)", "RR Interval, Aggregate (msec)".

Table to include post-baseline visits of "Week 2", "Week 4", "Week 10", "3-Week Follow-up", "5-Week Follow-up", "Latest Follow-up".

Table 14.3.1.5.1.3: Shift Summary of Overall Electrocardiogram (ECG) Assessments (Safety Population)
(Page 1 of 2)

Overall ECG Assessment (per Investigator)		Placebo (N=xxx)			Serlopitant 5 mg (N=xxx)	
- "		Week 2	.1 1 22		Week 2	
Baseline	Normal	Abnormal, NCS	Abnormal, CS	Normal	Abnormal, NCS	Abnormal, CS
Normal	xx ( xx.x%)	xx ( xx.x%)	xx ( xx.x%)	xx ( xx.x%)	xx ( xx.x%)	xx ( xx.x%)
Abnormal, NCS	xx ( xx.x%)	xx ( xx.x%)	xx ( xx.x%)	xx ( xx.x%)	xx ( xx.x%)	xx ( xx.x%)
Abnormal, CS	xx ( xx.x%)	xx ( xx.x%)	xx ( xx.x%)	xx ( xx.x%)	xx ( xx.x%)	xx ( xx.x%)
		Week 4			Week 4	
Baseline	Normal	Abnormal, NCS	Abnormal, CS	Normal	Abnormal, NCS	Abnormal, CS
Normal	xx ( xx.x%)	xx ( xx.x%)	xx ( xx.x%)	xx ( xx.x%)	xx ( xx.x%)	xx ( xx.x%)
Abnormal, NCS	xx ( xx.x%)	xx ( xx.x%)	xx ( xx.x%)	xx ( xx.x%)	xx ( xx.x%)	xx ( xx.x%)
Abnormal, CS	xx (xx.x%)	xx ( xx.x%)	xx ( xx.x%)	xx ( xx.x%)	xx ( xx.x%)	xx ( xx.x%)
		Week 10			Week 10	
Baseline	Normal	Abnormal, NCS	Abnormal, CS	Normal	Abnormal, NCS	Abnormal, CS
Normal	xx ( xx.x%)	xx ( xx.x%)	xx ( xx.x%)	xx ( xx.x%)	xx ( xx.x%)	xx ( xx.x%)
Abnormal, NCS	xx ( xx.x%)	xx ( xx.x%)	xx ( xx.x%)	xx ( xx.x%)	xx ( xx.x%)	xx ( xx.x%)
Abnormal, CS	xx ( xx.x%)	xx ( xx.x%)	xx ( xx.x%)	xx ( xx.x%)	xx ( xx.x%)	xx ( xx.x%)
	3	-Week Follow-up		3	-Week Follow-up	
Baseline	Normal	Abnormal, NCS	Abnormal, CS	Normal	Abnormal, NCS	Abnormal, CS
Normal	xx (xx.x%)	xx ( xx.x%)	xx ( xx.x%)	xx ( xx.x%)	xx (xx.x%)	xx ( xx.x%)
Abnormal, NCS	xx (xx.x%)	xx ( xx.x%)	xx ( xx.x%)	xx ( xx.x%)	xx ( xx.x%)	xx ( xx.x%)
Abnormal, CS	xx ( xx.x%)	xx ( xx.x%)	xx ( xx.x%)	xx ( xx.x%)	xx ( xx.x%)	xx ( xx.x%)
	5	-Week Follow-up		5	-Week Follow-up	
Baseline	Normal	Abnormal, NCS	Abnormal, CS	Normal	Abnormal, NCS	Abnormal, CS
Normal	xx ( xx.x%)	xx ( xx.x%)	xx ( xx.x%)	xx ( xx.x%)	xx ( xx.x%)	xx ( xx.x%)
Abnormal, NCS	xx ( xx.x%)	xx ( xx.x%)	xx ( xx.x%)	xx ( xx.x%)	xx ( xx.x%)	xx ( xx.x%)
Abnormal, CS	xx ( xx.x%)	xx ( xx.x%)	xx ( xx.x%)	xx ( xx.x%)	xx ( xx.x%)	xx ( xx.x%)

Note: No imputation of missing values. Baseline is the latest recorded value prior to first dose of study drug. "Latest Follow-up" visit includes the latest available follow-up information for each subject from the 3-Week or 5-Week Follow-up visits.

NCS=Not Clinically Significant; CS=Clinically Significant.

SOURCE: USERNAME\SPONSOR\PROJECT\JOBNAME (DATE,TIME)

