NK₁-R antagonist dependence has not previously been described and therefore a drug class-specific, reliable and sensitive instrument for the assessment of withdrawal symptoms has not been developed. A surrogate assessment tool, such as those developed for opioid or benzodiazepine dependence, is not available.

In order to provide a comprehensive set of assessments for physical dependence and withdrawal symptoms following chronic exposure to the study drug, the HADS and ESS instruments will be administered at baseline and throughout the study period, as well as 3-days and 7-days following the last dose of study drug, and then weekly throughout the 5-week post-study drug observation period. In addition, vital signs will be assessed at each post-study drug observation visit, and an ECG and laboratory analyses will be assessed at the

5-week post-study drug visit. All TEAEs reported during this period will be medically reviewed to assess for possible physical dependence or withdrawal signs or symptoms.

[figure not shown]

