### 6.9.4.7 Potential for Physical Dependence

In order to assess physical dependence and withdrawal, data collected during a 5-week post-drug observation period will be summarized. For each assessment, an on-drug baseline value is defined as Week 10 (for subjects completing treatment) or the last observation prior to last dose of study drug (for subjects that discontinued treatment early).

The observed data and change from on-drug baseline for the HADS will be summarized with descriptive statistics by time point (3-Day Follow-up, and 1-, 2-, 3-, 4- and 5-Week Follow-up). Both the Depression and the Anxiety subscales will be reported.

The observed data and change from on-drug baseline for the ESS will be summarized with descriptive statistics by time point (3-Day Follow-up, and 1-, 2-, 3-, 4- and 5-Week Follow-up).

Vital signs including change from on-drug baseline will be summarized with descriptive statistics for each post-study drug observation visit.

Overall ECG assessments (abnormal or normal), as well as observed and change from on-drug baseline for ECG parameters, will be summarized for the 5-week post-study drug visit. In addition, a summary of how many subjects developed a post-drug abnormal result will be presented.

Assessment of AEs reported after study drug discontinuation, i.e. during the post-study drug observation period, will be summarized separately by treatment group. AEs during the post-study drug observation period will be summarized by weekly periods and sex.

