Preferred Term	Likely Related	xx ( xx.x%)	xx ( xx.x%)
	Likely Unrelated	xx ( xx.x%)	xx ( xx.x%)
Preferred Term	Likely Related	xx ( xx.x%)	xx ( xx.x%)
	Likely Unrelated	xx ( xx.x%)	xx ( xx.x%)

<sup>a Counts reflect numbers of subjects reporting one or more TEAEs that map to MedDRA. At each level of summarization (System Organ Class or Preferred Term) subjects are counted once under the greatest reported relationship.

Note: TEAEs are AEs with an onset after first dose of study drug.

MedDRA Version 21.1.

Table 14.3.1.2.1.1: Overall Summary of Post-Drug Adverse Event (AEs) (Safety Population)

		Placebo			Serlopitant 5 mg	
	Males	Females	Overall	Males	Females	Overall
	(N=xxx)	(N=xxx)	(N=xxx)	(N=xxx)	(N=xxx)	(N=xxx)
Subjects with any Post-Drug AE	xx ( xx.x%)	xx ( xx.x%)				
Number of Post-Drug AEs	XX	XX	XX	XX	XX	XX
Subjects with any Related Post-Drug AE	xx ( xx.x%)	xx ( xx.x%)				
Number of Related Post-Drug AEs	XX	XX	XX	XX	XX	XX
Subjects with any Serious Post-Drug AE	xx ( xx.x%)	xx ( xx.x%)				
Number of Serious Post-Drug AEs	XX	XX	xx	xx	XX	XX
Subjects with any Related Serious Post-Drug AE	xx ( xx.x%)	xx ( xx.x%)				
Number of Related Serious Post-Drug AEs	XX	xx	xx	xx	xx	XX
Subjects who Died	xx ( xx.x%)	xx ( xx.x%)				
Maximum Severity by Subject						
Grade 5	xx ( xx.x%)	xx ( xx.x%)				
Grade 4	xx ( xx.x%)	xx ( xx.x%)				
Grade 3	xx ( xx.x%)	xx ( xx.x%)				
Grade 2	xx ( xx.x%)	xx ( xx.x%)				
Grade 1	xx ( xx.x%)	xx ( xx.x%)				
Maximum Relationship by Subject						
Likely Related	xx ( xx.x%)	xx ( xx.x%)				
Likely Unrelated	xx ( xx.x%)	xx ( xx.x%)				

Note: Table includes AEs with an onset after last dose of study drug.

Table 14.3.1.2.1.2: Overall Summary of Post-Drug Adverse Events (AEs) Occurring 1-7 Days Post Last Dose (Safety Population)

	Placebo	Serlopitant 5 mg
	(N=xxx)	(N=xxx)
Subjects with any Post-Drug AE	xx ( xx.x%)	xx (xx.x%)
Number of Post-Drug AEs	XX	XX
Subjects with any Related Post-Drug AE	xx ( xx.x%)	xx ( xx.x%)
Number of Related Post-Drug AEs	XX	XX
Subjects with any Serious Post-Drug AE	xx ( xx.x%)	xx ( xx.x%)
Number of Serious Post-Drug AEs	xx	XX
Subjects with any Related Serious Post-Drug AE	xx ( xx.x%)	xx ( xx.x%)
Number of Related Serious Post-Drug AEs	XX	XX
Subjects who Died	xx ( xx.x%)	xx ( xx.x%)
Maximum Severity by Subject		
Grade 5	xx ( xx.x%)	xx (xx.x%)
Grade 4	xx ( xx.x%)	xx ( xx.x%)
Grade 3	xx ( xx.x%)	xx ( xx.x%)
Grade 2	xx ( xx.x%)	xx (xx.x%)
Grade 1	xx ( xx.x%)	xx ( xx.x%)

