Maximum Relationship by Subject		
Likely Related	xx ( xx.x%)	xx (xx.x%)
Likely Unrelated	xx ( xx.x%)	$xx(x_0,x_0)$

Note: Table includes AEs with an onset date within 1 to 7 days after last dose of study drug. SOURCE: USERNAME\SPONSOR\PROJECT\JOBNAME (DATE,TIME)

Repeat Table 14.3.1.2.1.2 for the following, with adjusted foonotes:

Table 14.3.1.2.1.3: Overall Summary of Post-Drug Adverse Events (AEs) Occurring 8-14 Days Post Last Dose (Safety Population)

Note: Table includes AEs with an onset date within 8 to 14 days after last dose of study drug.

Table 14.3.1.2.1.4: Overall Summary of Post-Drug Adverse Events (AEs) Occurring 15-21 Days Post Last Dose (Safety Population)

Note: Table includes AEs with an onset date within 15 to 21 days after last dose of study drug.

Table 14.3.1.2.1.5: Overall Summary of Post-Drug Adverse Events (AEs) Occurring 22-28 Days Post Last Dose (Safety Population)

Note: Table includes AEs with an onset date within 22 to 28 days after last dose of study drug.

Table 14.3.1.2.1.6: Overall Summary of Post-Drug Adverse Events (AEs) Occurring 29-35 Days Post Last Dose (Safety Population)

Note: Table includes AEs with an onset date within 29 to 35 days after last dose of study drug.

Statistical Analysis Plan for Menlo Therapeutics Inc. Protocol Number: MTI-105

Table 14.3.1.2.2.1: Summary of Subjects Reporting Post-Drug Adverse Events (AEs) by MedDRA System Organ Class and Preferred Term (Safety Population)

(Page 1 of xx)

		Placebo			Serlopitant 5 mg	
System Organ Class a Preferred Term	Males (N=xxx)	Females (N=xxx)	Overall (N=xxx)	Males (N=xxx)	Females (N=xxx)	Overall (N=xxx)
Total	xx ( xx.x%)					
System Organ Class Preferred Term Preferred Term Preferred Term Preferred Term	xx ( xx.x%) xx ( xx.x%) xx ( xx.x%) xx ( xx.x%) xx ( xx.x%)	xx ( xx.x%) xx ( xx.x%) xx ( xx.x%) xx ( xx.x%) xx ( xx.x%)	xx ( xx.x%) xx ( xx.x%) xx ( xx.x%) xx ( xx.x%) xx ( xx.x%)	xx ( xx.x%) xx ( xx.x%) xx ( xx.x%) xx ( xx.x%) xx ( xx.x%)	xx ( xx.x%) xx ( xx.x%) xx ( xx.x%) xx ( xx.x%) xx ( xx.x%)	xx ( xx.x%) xx ( xx.x%) xx ( xx.x%) xx ( xx.x%) xx ( xx.x%)

<sup>a Counts reflect numbers of subjects reporting one or more AEs that map to MedDRA. At each level of summarization (System Organ Class or Preferred Term) subjects are counted once.

Note: Table includes AEs with an onset after last dose of study drug.

MedDRA Version 21.1.

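### The protocol's withdrawal review of post-drug adverse events has no by-arm display in the SAP and no requirement that it be finished before unblinding

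*SAP*

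**What the plan says.** Whether serlopitant produces physical dependence is a safety objective (Protocol 2, SAP 3) and a safety endpoint (Protocol 3.3.4, SAP 5.2). Protocol 6.2.7 explains that for this drug class a "reliable and sensitive instrument for the assessment of withdrawal symptoms has not been developed". It sets up HADS, ESS, vital signs, ECG and laboratory tests after the last dose, and adds: "All TEAEs reported during this period will be medically reviewed to assess for possible physical dependence or withdrawal signs or symptoms".

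On analysis, SAP 6.9.4.7 repeats Protocol 8.10.9: "Assessment of AEs reported after study drug discontinuation, i.e. during the post-study drug observation period, will be summarized separately by treatment group". It then adds: "AEs during the post-study drug observation period will be summarized by weekly periods and sex". SAP 8 declares no changes to the planned analyses.

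The shells in SAP 10 that carry this out are:

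- "Table 14.3.1.2.1.1: Overall Summary of Post-Drug Adverse Event (AEs) (Safety Population"), with rows for any, related, serious and related-serious events, deaths, maximum severity and maximum relationship, and five weekly companions (Tables 14.3.1.2.1.2 to 14.3.1.2.1.6);
- "Table 14.3.1.2.2.1: Summary of Subjects Reporting Post-Drug Adverse Events (AEs) by MedDRA System Organ Class and Preferred Term (Safety Population"), with a total row, organ-class rows and term rows, and weekly companions;
- matching tables by severity and by relationship.

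**The concern.** The protocol plans a specific judgement on each post-drug event: could this be withdrawal? The SAP has nowhere to put the answer. No shell counts subjects with an event so judged. The adverse event listings (16.2.7.1.2 and 16.2.7.1.3) have no field for it. No text gives criteria, or says the judgement is made and locked before treatment codes are known.

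This matters because withdrawal symptoms can spread over many terms and several organ classes (anxiety, insomnia, nausea and headache are my examples, not the documents'). A few extra subjects under each term are hard to see term by term, and they are mixed with unrelated events in the broader rows. If terms are grouped only after unblinding, either a finding of withdrawal or its dismissal can be charged with selection.

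**Working it through.** **Which planned displays could carry the review result?**

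| Display | What it counts | Withdrawal judgement? |
|---|---|---|
| Overall post-drug summary and weekly versions | any, related and serious events; maximum severity and relationship | No |
| Organ class and preferred term | subjects once per level, plus a total | No |
| Severity tables | grade | No |
| Relationship tables | investigator causality | No |
| Event listings | term, dates, grade, relationship, outcome, seriousness, action | No |

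The row "Subjects with any Related Post-Drug AE" is the closest, but it answers another question. Protocol 7.2.4 defines a likely related event by its timing after administration, a known or expected response pattern, and other causes being less likely. A withdrawal symptom follows stopping, and Protocol 6.2.7 says dependence has not been described for this class. Such an event could reasonably be classed as likely unrelated.

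**How much dilution?** The documents give no post-drug event rates, no power figure for this comparison and no planned test, so there is no figure of theirs to reproduce. Power is used here only as a measure of visibility.

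Inputs: 140 per arm (Protocol 8.1, SAP 7). Assumed: six independent withdrawal-type terms, each at 0.5% on placebo and 1.5% on serlopitant; unrelated events in 15% or 30% of subjects in both arms.

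- One term: 140 × 0.005 = 0.7 against 140 × 0.015 = 2.1 expected subjects.
- Pooled row, 1 − (1 − p)^6: 1 − 0.995^6 = 3.0% and 1 − 0.985^6 = 8.7%, or about 4.1 against 12.1 subjects.
- Any-event row with unrelated rate b and pooled rate c, 1 − (1 − b)(1 − c): for b = 15%, 17.5% against 22.4%; for b = 30%, 32.1% against 36.1%.

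| Row | Placebo | Serlopitant | Exact Fisher power, two-sided 5% |
|---|---|---|---|
| One term | 0.5% | 1.5% | 1% |
| Pooled withdrawal row | 3.0% | 8.7% | 43% |
| Any event, 15% unrelated | 17.5% | 22.4% | 14% |
| Any event, 30% unrelated | 32.1% | 36.1% | 9% |

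**Range.** With 5 to 10 terms and term rates of 1% against 2%, 1% against 3%, or 0.5% against 2%, power is 2 to 8% for one term and 25 to 95% for the pooled row. For the any-event row it is 10 to 69% with 15% unrelated events and 7 to 45% with 30%. In each scenario the order is the same: pooled row, then any-event row, then single term.

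**The case against.** The strongest reply is that much is already planned. A reader might infer that post-drug events are tabulated only by single preferred term. They are not: the term table has total and organ-class rows ("At each level of summarization (System Organ Class or Preferred Term) subjects are counted once"), and the overall summaries give any-event counts by arm and by week. HADS, ESS, vital signs and ECG are also compared with an on-drug baseline, and HADS scores anxiety and depression directly. All of this stands, and it rules out calling a withdrawal signal invisible. The reply has a limit, though. The tables against on-drug baseline cover only subjects consenting to Protocol Version 3.0, whereas the post-drug event tables cover the whole Safety Population. The whole-population HADS and ESS tables show only three-week, five-week and latest follow-up, against pre-treatment baseline.

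Second, the protocol promises a review, not a table, and the sentence on assessment of post-drug events can be read as meaning the event tables themselves. That reading is possible, so I do not say the SAP breaks a protocol commitment. It still leaves the review without a planned display.

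Third, a reader might infer that the judgement would be made unblinded. The documents do not support that: the sponsor and investigators are blinded (Protocol 5.8.2) and an internal team monitors blinded safety data (Protocol 3.4.1). The narrower point stands: no text assigns this review to that team, requires its outcome to be recorded, or sets its completion before unblinding.

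Fourth, a bare flag moves the subjectivity to the reviewer and counts one isolated headache like a cluster of symptoms. That is fair, and it is why the fix needs criteria set in advance.

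**Conclusion.** The point holds as a reporting and prespecification gap on a stated objective. The outcome of the protocol's withdrawal review has no planned by-arm display, no criteria and no requirement to be complete before unblinding. A diffuse syndrome would show only in non-specific total, any-event or organ-class rows, in sparse term rows, or in part through HADS, ESS, vital signs and ECG.

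The size is illustrative. It rests on assumed rates, on independence between terms, and on a test the plan does not include. If symptoms cluster in the same subjects, the pooled row counts fewer subjects and its advantage shrinks. Even in the worked example the pooled row would miss the assumed excess more often than not (43% power). The case for change is that the pooled row is clearer than the planned rows and free of after-the-fact grouping, not that it would settle the question. It is a worthwhile, cheap improvement; the primary efficacy analysis is not affected.

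**What to change.** In SAP 6.9.4.7, state that the Protocol 6.2.7 review is done blinded, against criteria or a term list fixed in advance, and locked before unblinding, with each post-drug event flagged yes or no as a possible withdrawal sign or symptom.

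Add a by-arm row, subjects with any possible withdrawal AE, to Table 14.3.1.2.1.1, and the same count to weekly Tables 14.3.1.2.1.2 to 14.3.1.2.1.6. Keep it descriptive; a risk difference with 95% confidence interval is optional. A count of subjects with more than one flagged event would help separate a cluster from an isolated symptom. Carry the flag into the event listings.

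The cost is a short addition to the SAP text, one flag variable from a review already planned, and one row in six shells. No visit, assessment or treatment changes. The one real burden is that the criteria must be written and the review finished before unblinding.
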